**Procedure and measures:** The procedure for this research has been based on the recent work by Bulkeley, Bundy, Roberts, and Einfeld (2016). Similarly to Bulkeley et al. (2016), an A-B-A SCD will be used over a 9 week period (see figure 1). The A-B-A design will allow for an initial baseline measurement (A1), the intervention period (B) and a return-to-baseline phase (A2). Following screening of a sensory over-responsiveness, the initial baseline (A1) will occur for 2 weeks, whereby the parent will rate their child's target undesirable behaviour at the conclusion of each day. Next, during the 5-week intervention phase (B), the researcher, who is an experienced and practicing occupational therapist, will visit 5 times to individually provide the participants with education, programming, modelling and follow up. During the 'B' phase the parent will continue to rate the target behaviour daily. Lastly, the return-to-baseline (A2) will involve the parent ceasing proprioceptive activities (intervention) and continuing to score the target behaviour daily. The A-B-A design allows for the functional link between behaviour change and the intervention to be measured (Bulkeley et al., 2013; Kazdin, 2011).

Figure 1: Research Procedure

Prior to beginning the research phase (A-B-A), screening will take place to: 1) ensure the children in the study have sensory over-responsiveness (defined by sensory avoiding and/or

sensitivity behaviours as identified by Sensory Profile 2 Child; SP-2) and 2) to identify a target undesirable behaviour for each child. Screening will involve the researcher completing the SP-2 with each parent. Please see appendix A for copy of SP-2. This assessment is a questionnaire for age 3:0 to 14:11 years in which the caregiver marks how frequently the child engages in behaviours listed on the form. The SP-2 has demonstrated good validity and reliability (internal consistency, test-retest reliability and interrater reliability); with these psychometric properties inclusive of children with ASD (Dunn, 2014b). The norm-referenced results rate the child's responses (low registration, seeking, sensitivity, avoiding) in a range of sensory areas: auditory, visual, touch, movement, body position and oral sensory (Dunn, 2014a). If results from the SP-2 show the child as having "much more than others" response for avoiding and or sensitivity, meaning the child displays over-responsiveness, the child will be eligible for the study.

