**Data analysis:** Data analysis will involve visual analysis of the VAS results for each participant. As with SCD research, each child is his/her own control, and therefore, each child's data will be analysed individually. The visual analysis will aim to find a causal relationship between the intervention and the child's undesirable behaviour, and the strength of this relationships, then generate a hypothesis about the relationship (Kazdin, 2011; Kratochwill et al., 2013)

The first step in the visual analysis will be establishing a projected level of baseline (A1) data, that is, determining whether the target undesirable behaviour is steady, increasing, decreasing or adopting another pattern over the 2 weeks prior to intervention. Next, the data

within each child's B and A2 phase will be examined to establish the within-phase patterns. The data from each phase will then be compared visually to the data in the adjacent phase (A1 to B and B to A2). This will be done for each child and will determine if the addition of the proprioceptive intervention has an effect on undesirable behaviour. The final step will include integrating the information from each phase (A1, B and A2) to establish preliminary evidence of a causal relationship (Kratochwill et al., 2013).

Throughout the analysis phase, six outcome-measure features will be used to examine the within- and between-phase data patterns (Kratochwill et al., 2013): level (mean of the data points); trend (best-fitting straight line); variability (scatter of points); immediacy of the effect (immediate change in level of data points in adjacent phases); overlap (same data level in adjacent phases) and; consistency of data patterns across similar phases (similarity of data level, trend and variability in A1 and A2). Analysis of these six outcome measures across and within the phases, will support the argument for preliminary evidence of a causal relationship between parent-facilitated, responsive proprioceptive input and undesirable behaviours for children with ASD and co-occurring sensory over-responsiveness.

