## 10. TIMELINES / MILESTONES

**Timeline** (July 2017 – July 2018)

Date	Phase	Participant Tasks	Researcher Tasks
July 18 th	Ethics approval	
 
○ N/a
 
	
 
○ Submit ethics
 

< August 13 th	Preparation - find potential participants	
 
○ Email interest
 
	
 
○ Distribute flyer
 
○ Phone potential participants to ensure they meet eligibility criteria
 

< August 13 th	Preparation – screen potential participants	
 
○ Read PIS and consent form – ask questions
 
○ Complete Sensory Profile 2 online
 
	
 
○ Email PIS and consent form – answer questions
 
○ Email Sensory Profile 2 Online
 

< August 13 th	Preparation – recruit eligible participants	
 
○ Parent and child sign consent form
 
	
 
○ Formulate target behaviour and outcome measure (see below)
 
○ Set up PIEL Survey (specific to each family)
 

August 14 th - August 27 th	Phase A1 (2 weeks)	
 
○ Parent scores behaviour daily
 
	
 
○ No home visits (unless need support to use PIEL Survey)
 

August 28 th – October 1 st	Phase B (5 weeks)	
 
○ Parent implements proprioceptive activities as per individual family plan (see below)
 
○ Parent scores behaviour daily
 
	
 
○ Provide education to family (see handout below)
 
○ Create individual family plan (see below)
 
○ Home visits 1/week
 

October 2 nd – October 15 th	Phase A2 (2 weeks)	
 
○ Parent scores behaviour daily
 
	
 
○ Reminder to participant to stop all proprioceptive intervention
 
○ No home visits
 

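### Phase B opens on a common date, but parents are first trained at a visit inside B whose day is not fixed, so ratings from before that visit are counted as intervention data.

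*Protocol*

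**What the plan says.** - **Phase lengths.** Protocol Section 6 (Procedure and measures) states that "the initial baseline (A1) will occur for 2 weeks". Phase B then lasts five weeks, with daily parent ratings throughout, followed by the return-to-baseline phase A2.
- **Dates.** Section 10 gives B one calendar for all families: "August 28 th – October 1 st".
- **Where training sits.** In Section 6 the researcher "will visit 5 times to individually provide the participants with education, programming, modelling and follow up", all within B. The phase B row of Section 10 lists the researcher's tasks as "Provide education to family (see handout below", "Create individual family plan (see below" and "Home visits 1/week". The A1 row allows a visit only to help with the survey app.
- **What counts as treatment.** Section 6 (Study Design) describes the condition under test as parent-delivered, responsive proprioceptive input. Section 2 says that parents deliver it after training by the researcher.
- **Visit timing.** Section 6 (Intervention) asks for weekly visits in B, ideally when the target behaviour is likely to occur. It does not say on which day of B the first visit falls.
- **Analysis.** Two of the six features in Section 6 (Data analysis) are "level (mean of the data points" and "immediacy of the effect (immediate change in level of data points in adjacent phases". A third is trend, as a best-fitting straight line. None of them refers to the date of the first visit.

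**The concern.** The start of B is set by the calendar, while the start of the intervention is set by the researcher's diary. Where the two differ, the first B ratings describe a child who has had neither the training package nor the input. Those ratings enter the B mean, the B trend line and the first B points that are compared with A1.

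The distortion of level and immediacy is towards no effect, and its size varies between children for a reason unrelated to response. Each child has only two phase changes, and Section 6 already concedes that an A-B-A design falls short of the recommended three demonstrations of effect. Blurring the A1-to-B change therefore costs more here than it would in a design with more phase changes.

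**Working it through.** **Calendar.** Section 10 gives A1 as 14–27 August (14 days), B as 28 August–1 October (35 days) and A2 as 2–15 October (14 days). 14 + 35 + 14 = 63 days = 9 weeks, which reproduces the stated research period.

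**Model.** Assume that the intervention produces an immediate, lasting drop in the rating from the day *k* of B on which the family is first visited. Then *m* = *k* − 1 days of B are untreated. The visit day counts as treated because the rating is made that night. Weekly visits put *k* between 1 and 7 if the first visit falls in week 1. The immediacy window *w* is not stated, so 3, 5 and 7 points are shown as assumptions.

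- Untreated share of B = *m*/35
- Share of the effect kept in the B mean = (35 − *m*)/35
- Share of the effect kept in the first *w* points = max(0, *w* − *m*)/*w*
- Spurious fitted drop across B, in units of the effect = 34 × [*m*(35 − *m*)/2]/3570, where 3570 = 35 × (35² − 1)/12 is the sum of squares of the day numbers about their mean

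Example for *k* = 4 (*m* = 3): untreated 3/35 = 8.6%; level kept 32/35 = 91.4%; three-point immediacy (3 − 3)/3 = 0; fitted drop 34 × 48/3570 = 0.46.

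| First visit on B day | Untreated B days | Share of B | Level kept | Immediacy kept, *w* = 3 | *w* = 5 | *w* = 7 | Fitted drop over B |
|---|---|---|---|---|---|---|---|
| 1 | 0 | 0% | 100% | 100% | 100% | 100% | 0 |
| 2 | 1 | 2.9% | 97.1% | 67% | 80% | 86% | 0.16 |
| 3 | 2 | 5.7% | 94.3% | 33% | 60% | 71% | 0.31 |
| 4 | 3 | 8.6% | 91.4% | 0% | 40% | 57% | 0.46 |
| 5 | 4 | 11.4% | 88.6% | 0% | 20% | 43% | 0.59 |
| 6 | 5 | 14.3% | 85.7% | 0% | 0% | 29% | 0.71 |
| 7 | 6 | 17.1% | 82.9% | 0% | 0% | 14% | 0.83 |

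**Illustration across the five families.** 28 August 2017 is a Monday. If one family were first visited on each weekday (an assumption), the untreated days would be 0, 1, 2, 3 and 4, a mean of 2/35 = 5.7% of B. Three-point immediacy would keep 100, 67, 33, 0 and 0% of the effect.

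**With B starting at the first visit.** *m* = 0 for every child, so under the same model level and immediacy keep 100% and no spurious trend arises.

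**The case against.** **Training belongs to B by design.** Section 6 (Intervention) makes education, programming, modelling and follow-up part of the intervention phase. A reader might infer that every day of training or learning is wrongly counted as treated. The documents do not support that: gradual uptake after the first visit is part of the package being studied. Only the days before the first visit are at issue.

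**A day-1 visit is possible.** Five weekly visits in five weeks are compatible with a first visit on B day 1, and Figure 1 of the protocol, which might place the visits, is not shown in the text available. A reader might infer that immediacy is zero by construction, or that two of the five children are bound to show none. Neither follows. Zero needs both a late first visit and a short window, it refers to the expected change, and observed ratings will still vary. The two-of-five count comes only from the assumed weekday schedule and three-point window.

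**The loss is modest and visible.** The level loss is small, immediacy at B-to-A2 is untouched, and an analyst who knows the visit dates could see a delayed step on the plot. All of this stands. But the stated features do not use visit dates, and the protocol does not say that they are recorded.

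**It could be left to an analysis plan.** That is fair for the immediacy window. The phase boundary and the placement of training are design features that the protocol itself fixes.

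**Conclusion.** The concern holds in a limited form. The protocol ties B to a common date and places the first training inside B without fixing its day, so any family not visited on B day 1 contributes untreated ratings to B.

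For a first visit in week 1, this affects at most 6 of 35 days. The B mean then keeps at least 83% of the effect, a minor loss. The distortion of immediacy and trend can be larger: three-point immediacy has expected value zero from a day-4 visit onward, five-point immediacy from day 6, and the spurious fitted drop reaches 0.83 of the effect at day 7. A first visit on day 1 causes no such loss.

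These figures assume an immediate step effect, a first visit in week 1 and windows that the protocol does not state. That untreated days can be labelled B follows from Sections 2, 6 and 10 without those assumptions.

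**What to change.** - In Section 6 (Procedure and measures) and Section 10, define each child's B day 1 as the day of that family's first education and modelling visit. Keep all earlier ratings in A1 and record the visit date.
- Let B run five weeks from that day, with the two weeks of A2 following, so that every child keeps 35 B days and 14 A2 days.
- In Section 6 (Data analysis), read A1-to-B immediacy from that B day 1. Training days after the first visit stay in B as part of the package.

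I would not go further and restrict the level comparison to a late part of B. Using only the last 14 days, for example, would discard 21 of 35 ratings, separate the compared data from A1 by about three weeks, and favour slow drift.

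**Cost.** The change needs protocol wording and five recorded dates. For a first visit within a week of 28 August, A1 grows by up to 6 days (14 to at most 20). The participation period grows from 63 to at most 69 days, so A2 ends by 21 October at the latest. A1 length and end dates will differ by a few days between children, and the nine-week period told to families needs matching wording.

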The researcher and parent will identify a target undesirable behaviour (that is a result of sensory over-responsiveness) from a sensory domain of SP-2 where the child responded 'much more than others'. For example, if the child scores 'much more than others' in the area of touch, the researcher will refer to the 'almost always' and 'frequently' answers for the questions asked about touch. This will show what behaviours, related to sensory touch, are impacting the most on the the child and their family's day to day lives. Using the touch example, a target behaviour deduced from the SP-2 may be 'shows an emotional or aggressive response to being touched'. The impact (e.g. level of aggression from touch) of the target behaviour will be rated by the parent daily during the research period.

SCD research requires ongoing monitoring to effectively track individual outcomes (Mesibov & Shea, 2011). A Visual Analogue Scale (VAS) will be used to track the child's behaviour throughout the research period. Please see appendix B for copy for VAS. The VAS is the chosen instrument because it is individualised, user friendly, inexpensive and has good reliability and construct validity (Chafouleas, Sanetti, Kilgus, & Maggin, 2012; Wewers & Lowe, 1990). The VAS will be individualised for each participant, for example, using the behaviour defined above, the VAS would record parent daily perceptions from 'no aggression to 'high aggression'. To ensure consistency in the recognition of the target behaviour, the same parent will score the behaviour throughout the research period and a clear description of the behaviour will be provided on each VAS. Each night, parents will be required to 1) indicate whether the child presents the undesirable behaviour that day, and 2) mark on a line how they perceived the impact of the target behaviour that day. To make rating accessible and efficient, parents will use the application P.I.E.L. Survey (Jessup, Bian, Chen, & Bundy, 2012) where they will be able to access their individualised VAS each day. The parents will be able to loan an iPod touch from The University of Sydney if they do not have own a compatible iOS device. Using P.I.E.L. Survey allows the researchers to download all the participant's responses. By utilising a VAS, a parent-rated assessment measure, the effects of the researcher also being the interventionalist are minimised.

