The design of this SCD research study mimics real life therapy strategies whereby parents implement intervention throughout the day with their child. However, to analyse a causal relationship between the intervention and the undesirable behaviours, evaluation at the end of each day which encompasses the parent's perceptions of their child's behaviour throughout the day is included.

**Intervention:** In line SCD research, the intervention has been developed to reflect real world occupational therapy with an aim of being easily embedded into regular routines, with minimal additional demands for participants. Furthermore, each participant is able to work towards an outcome meaningful to them. Each child has their own target behaviour which is measured using the VAS and their own set of proprioceptive activities that work for their family. However, important to the research design is the consistency of proprioceptive input being received by the child in the set activities (Mesibov, 2011). Therefore, to ensure each child is correctly receiving proprioceptive input, the intervention phase includes: education, programming, modelling and follow up.

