Education will involve the researcher (occupational therapist) explaining the fundamentals of sensory over-responsiveness to parents and how to be responsive through understanding the signs of over-responsiveness and triggers for the child's target behaviour. The researcher will work with the parent to develop a program of activities that primarily provide proprioceptive input to the body. These activities will be those that can easily be implemented in the home environment and in the child's established routine, typically embedded within play or jobs around the house. The recommended activities do not involve expensive equipment or specialised training to administer. The parent will facilitate the proprioceptive activities when triggers of the target behaviour are present or when they observe the child showing signs of over-responsiveness. Please see appendix C for parent handout. The researcher will model how to engage the child in these activities and how to perform the activities correctly in order to provide proprioceptive input. The parent will facilitate the activities for 10-15 minutes, or until they see a positive change in the child's face and body language. This time frame was chosen as it is a commonly used time frame for implementing sensory based intervention (e.g. Bagatell et al., 2010; Escalona et al., 2001; Reichow et al., 2010; Schilling & Schwartz, 2004; Silva et al., 2009). The researcher will visit the home weekly during the intervention 'B' phase, ideally when the target behaviour is expected to occur, to follow up and provide further guidance to the parents.

Due to the target behaviour being a behaviour scored as 'always' or 'frequently' on the SP-2, it is anticipated the behaviour will occur almost, if not, daily and may even occur numerous times a day. It is not anticipated that the intervention will remove the behaviour altogether, but rather, from being responsive to the child's signs of entering high arousal and becoming over-responsive to certain sensory stimuli, the perceived impact of undesirable behaviour will be minimised.

**Expected duration of study:** The research period for each participant is 9 weeks. The total length of the study will be from July 2017 to July 2018.

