**Use these guidelines to mark your responses.**

When presented with the opportunity, my child...

responds in this manner **Almost Always** (90% or more of the time)

responds in this manner **Frequently** (75% of the time)

responds in this manner **Half the Time** (50% of the time)

responds in this manner **Occasionally** (25% of the time)

responds in this manner **Almost Never** (10% or less of the time)

If you are unable to answer because you have not observed the behavior or believe it does not apply to your child, please click **Does Not Apply**.

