**16. shows distress during grooming (for example, fights or cries during haircutting, face washing, fingernail cutting)**

**Almost Always Frequently Half the Time Occasionally Almost Never Does Not Apply**

**17. becomes irritated by wearing shoes or socks**

**Almost Always Frequently Half the Time Occasionally Almost Never Does Not Apply**

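### The SP-2 score does not show that the target behaviour will occur almost daily, and the nightly record cannot tell a day without a trigger from a day when the trigger caused no reaction

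*Protocol*

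**What the plan says.** Section 6 (Intervention) gives its forecast and its reason in one sentence. The reason is "Due to the target behaviour being a behaviour scored as 'always' or 'frequently' on the SP-2", and the forecast is "it is anticipated the behaviour will occur almost, if not, daily and may even occur numerous times a day".

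The SP-2 instructions in Appendix A begin each response with "When presented with the opportunity, my child". Almost Always is then defined as "90% or more of the time", and Frequently as 75%.

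The target is chosen in section 6 (Procedure and measures). In the worked example on touch, "the researcher will refer to the 'almost always' and 'frequently' answers for the questions asked about touch". The aim is to find the behaviours that weigh most on the family's daily life. No minimum number of days or opportunities per week is set.

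Each night the parent is to "indicate whether the child presents the undesirable behaviour that day, and 2) mark on a line how they perceived the impact" of the behaviour. The rating is meant as an "evaluation at the end of each day which encompasses the parent's perceptions of their child's behaviour throughout the day". Section 6 (Data analysis) then compares A1, B and A2 for each child on level, trend, variability, immediacy, overlap and consistency, all taken from this one VAS series.

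**The concern.** An SP-2 answer is a conditional rate: how often the child reacts, given that the trigger is there. The forecast in section 6 is an unconditional rate: how many days show the behaviour. The second needs the frequency of the trigger, which the protocol neither states nor checks. Some SP-2 items mix routine and occasional triggers, for example "shows distress during grooming (for example, fights or cries during haircutting, face washing, fingernail cutting" among the touch items.

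The nightly record cannot repair this. A day marked as free of the behaviour may be a day on which the trigger arose and the child coped, which is the result the study hopes for. It may equally be a day on which nothing happened to react to, which carries no information about treatment. The VAS is the only outcome described, it is read child by child in five families, and there is no control series. A difference in exposure between phases would therefore appear as a difference in behaviour, in either direction. Exposure that was not recorded at the time cannot be reconstructed when the graphs are drawn.

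**Working it through.** The protocol gives no calculation on this point, so there is no figure to reproduce. The check asks what the SP-2 anchors imply for the number of behaviour days.

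**Inputs from the protocol.** A1 is 14 days, B is 35 and A2 is 14 (14 + 35 + 14 = 63 days, or 9 weeks). The reaction rate given an opportunity, p, is 0.75 (Frequently) or 0.90 (the floor of Almost Always).

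**Assumptions.** The share of days with one opportunity, e, ranges from 1/7 to 7/7. Days are independent. For phase means, a day without the behaviour scores 0 and a day with it scores a constant s.

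**Step 1: behaviour days in A1.** The chance of the behaviour on a given day is p × e, so the expected number in A1 is 14 × p × e. At 2 opportunity days a week and p = 0.75 this is 14 × 0.75 × 2/7 = 3.0. The chance of two or fewer behaviour days is the lower tail of Binomial(14, p × e).

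**Step 2: chance difference with no effect.** A simulation of 200,000 runs per setting drew behaviour days for A1 and B at the same exposure with zero treatment effect. It counted how often the B mean lay at least 30% below the A1 mean (an assumed yardstick).

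Each cell gives p = 0.75 / p = 0.90.

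| Opportunity days per week | Expected behaviour days in A1 (of 14) | Chance of 2 or fewer in A1 | Chance that B is at least 30% below A1, no effect |
|---|---|---|---|
| 1 | 1.5 / 1.8 | 0.82 / 0.74 | not run |
| 2 | 3.0 / 3.6 | 0.40 / 0.26 | 0.25 / 0.23 |
| 3 | 4.5 / 5.4 | 0.12 / 0.05 | 0.20 / 0.17 |
| 5 | 7.5 / 9.0 | 0.003 / below 0.001 | 0.10 / 0.06 |
| 7 | 10.5 / 12.6 | below 0.001 / below 0.001 | 0.02 / below 0.001 |

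Almost-daily behaviour is reached only when the opportunity itself is about daily. With two independent opportunities every day, the chance of at least one reaction is 1 − 0.25² = 0.94 at p = 0.75, or 1 − 0.10² = 0.99 at p = 0.90, and the forecast is met.

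**Step 3: exposure that differs between phases.** The expected phase mean is s × p × e. With no treatment effect, the relative change from A1 to B is e(B)/e(A1) − 1, whatever s and p are:

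- 5 to 3 days a week: 3/5 − 1 = −40%. With s = 60 and p = 0.75, the mean goes from 32.1 to 19.3.
- 6 to 5 days a week: 5/6 − 1 = −17%.
- 3 to 5 days a week: 5/3 − 1 = +67%, which could hide a real benefit.

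In the 5-to-3 case, the simulated chance that the B mean lies at least 30% below A1 is 0.67 / 0.69.

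**The case against.** Selection does not rest on the SP-2 category alone. Parent and researcher look for a behaviour that weighs on daily life, and the protocol's own example, reacting to touch, is plausibly an everyday event. The Individual Family Plan in Appendix C asks when the behaviour generally occurs and what triggers it. The SP-2 items with rare triggers also name routine ones: the grooming item includes face washing, and the loud-noise item includes barking dogs. This makes a rarely triggered target unlikely. It does not exclude one, because section 6 sets no frequency criterion and section 10 places the family plan in phase B, after the target has been chosen and A1 is over.

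The first nightly item does separate behaviour days from other days, so impact on behaviour days can be inspected. What it cannot do is split the other days into those with and without a trigger. The VAS form in Appendix B is a figure that is not shown, so a trigger item there cannot be ruled out, but section 6 lists only two items. Rules for scoring may sit in an analysis plan; whether exposure is recorded at all is a matter of data collection.

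Three stronger readings are tempting, and the documents do not support them:

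- *The VAS would mainly measure exposure.* That depends on trigger rates that the protocol does not give. At daily exposure it is not so.
- *Parents taught about triggers in B will avoid them and create a false benefit.* Section 6 and Appendix C tell parents to run the activities before or during triggers, not to avoid them. Avoidance that persisted into A2 would also spoil the return to baseline and the A1–A2 consistency that the analysis looks for.
- *Scarce triggers cut a standardised change of 1.0 to 0.36 at 5 trigger days a week.* That illustration (assumed impact 60, SD 15, benefit 15) has the child react on every trigger day, against the SP-2 anchors. At p = 0.75 with daily triggers, the shift is 0.75 × 15 = 11.25 and the variance is 0.75 × (15² + 60²) − 45² = 843.75. The SD is 29.05 and the ratio 0.39. At p = 0.90 the ratio is 13.5/22.95 = 0.59. Much of the apparent loss therefore does not come from scarce triggers.

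**Conclusion.** The inference in section 6 does not follow from the SP-2 as Appendix A defines it, and the nightly items listed cannot show afterwards whether the forecast held. The consequence is conditional: level, trend and overlap can partly reflect exposure if triggers are not near-daily or if exposure differs between phases. The 40% fall rests on an assumed drop from 5 to 3 trigger days a week, zero scores on days without the behaviour, and no treatment effect; a drop from 6 to 5 gives 17%. The table also rests on independent days and one opportunity per trigger day; a trigger on a fixed twice-weekly schedule would give exactly 4 trigger days in A1. The study claims only preliminary evidence, which limits the harm. The gap should still be closed before A1 begins, because it cannot be closed later.

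**What to change.** **Section 6, Procedure and measures.** At target selection, require the parent to report that the trigger arises at home on most days, for example at least 5 of 7. Add one nightly item: did the trigger occur today?

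**Section 6, Intervention.** Base the expectation of near-daily behaviour on that frequency check, not on the SP-2 category.

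**Section 6, Data analysis.** Keep the whole-day VAS series as the main analysis. Mark days without a trigger on each child's graph, compare the number of trigger days across A1, B and A2, and show the trigger-day series as a sensitivity display. It should not replace the main series, because the unblinded parent who delivers the intervention also reports exposure, so selecting on that report could bring in bias of its own. For the same reason the rating should not be narrowed to hours in the parent's care, which would change the whole-day measure the protocol chose on purpose.

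**Cost.** One more tap a night in an app that is already opened, and some protocol wording. A severe but rarely triggered behaviour could no longer be the target. The 5-of-7 threshold is a judgement and can be varied.

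### As worded, overlap asks only whether adjacent phases share the same mean, so one of the six visual-analysis features repeats level and says nothing about how daily ratings intermingle

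*Protocol*

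**What the plan says.** The Data analysis part of section 6 of the protocol plans a visual analysis of each child's daily VAS ratings, with adjacent phases compared (A1 with B, B with A2). One stated aim is to find "the strength of this relationships, then generate a hypothesis about the relationship".

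Six features are listed, each with a short gloss. The two that matter most for this point are the first and the fifth. The first is given as "level (mean of the data points"). The fifth, a few lines further down the same list, is given as "overlap (same data level in adjacent phases").

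Of the other four, trend is a straight line fitted to the ratings and variability is their spread. The fourth feature is worded as "immediacy of the effect (immediate change in level of data points in adjacent phases"). The last compares like with like, the two phases without intervention, and its gloss is "similarity of data level, trend and variability in A1 and A2".

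No other part of the protocol defines overlap by individual ratings or by a share of common values.

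**The concern.** Overlap should tell the reader how far the ratings in one phase lie among those of the next. It is the direct check on whether a difference in means stands clear of day-to-day noise. Defined through level, it cannot do this. Two phases with different means have no overlap however much their ratings mix, and two phases with equal means overlap whatever their scatter.

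Only immediacy and overlap are defined explicitly between adjacent phases, and both are worded in terms of level. Trend and variability describe a single phase. Consistency compares A1 with A2, which are not adjacent.

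This matters here because the Intervention part of section 6 expects the behaviour to lessen in impact, not to disappear. A partial shift in a daily rating is where the ratings of adjacent phases are likely to mix. If the written definition is followed, a modest shift in noisy ratings would be recorded as free of overlap.

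**Working it through.** **Step 1: substitution.** Level is the mean of the points in a phase. Overlap is the same level in adjacent phases. Therefore overlap means equal phase means in adjacent phases, which is the A1-B and B-A2 level comparison again. On a continuous scale two phase means almost never coincide, so the literal answer is nearly always that there is no overlap.

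**Step 2: what a point-based measure would show.** The protocol gives no figure for overlap to reproduce, and no SD or expected shift for the VAS. The values below are therefore assumptions: independent normal daily ratings, equal spread in both phases, lower being better, and a shift of d SDs. The non-overlap of all pairs (NAP) is the chance that a random B day is better than a random A1 day:

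NAP = Φ(d/√2)

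| Shift d (SD) | d/√2 | NAP | Pairs in wrong direction (1 − NAP) | Literal definition |
|---|---|---|---|---|
| 0.5 | 0.354 | 0.638 | 36% | no overlap |
| 1.0 | 0.707 | 0.760 | 24% | no overlap |
| 1.5 | 1.061 | 0.856 | 14% | no overlap |

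**Step 3: one mean shift with different scatter.** From section 6 and the section 10 timeline, A1 lasts 2 weeks (2 × 7 = 14 ratings) and B lasts 5 weeks (5 × 7 = 35 ratings). Assume a 0-100 scale with an A1 mean of 70 and a B mean of 50, and let the SD vary. NAP = Φ(20/(SD·√2)). The last column is the average share of the 35 B days below the lowest of the 14 A1 days, from 20,000 simulated series.

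| Assumed SD | NAP | B days below the whole A1 range |
|---|---|---|
| 5 | 0.998 | 98% |
| 10 | 0.921 | 61% |
| 20 | 0.760 | 27% |
| 30 | 0.681 | 18% |

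At SD 20, the two sample means differed in every one of a further 20,000 simulated series, so the literal definition reports no overlap each time. Yet every one of those series had at least one B day at or above the lowest A1 day. The same 20-point difference in means thus goes with almost complete separation or with heavy mixing, and the written definition does not distinguish them.

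**The case against.** The strongest reply is that level is not used strictly as the phase mean throughout. The first analysis step speaks of the level of the baseline and explains it as a pattern over time. The gloss on immediacy must refer to the height of points near the phase change, because a whole-phase mean cannot change immediately. On that usage, the same data level could mean data at the same height in both phases, which is ordinary overlap. An analyst who knows the method would probably read it so, if only because the literal reading leaves the feature almost empty. This reading is possible. But the protocol's own gloss in the same list makes the literal reading the more natural one, and the ambiguity is itself a reason to reword.

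A second reply is that an overlap index commonly belongs in a statistical analysis plan, which is not at hand. That is right for the choice of index, and its absence is not counted here. The point concerns a definition that the protocol does state. A later plan would either inherit it or contradict it.

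A reader might infer more: that the plan cannot assess strength at all, or that its verdict rests on means alone. The documents do not support this. Variability is listed beside level, and under the assumptions of step 2 NAP depends only on the mean shift divided by the SD, so those two features read together largely determine it. Immediacy and A1/A2 consistency also bear on strength, and it is the daily data of adjacent phases that are to be compared visually. Nor does the protocol state a rule that declares an effect when B has the lowest mean. Chance rates worked out for such a rule would not describe this plan.

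**Conclusion.** The point holds in a limited form. Read with the protocol's own definition of level, overlap duplicates the level comparison, and one of the six features is lost as worded. With shifts of 0.5 to 1.5 SD, between about 36% and 14% of day pairs would run the wrong way while the written definition records no overlap.

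Those percentages illustrate the gap and do not predict this trial's data. They rest on independent normal ratings of equal spread, and step 3 also rests on an assumed scale, assumed means and assumed SDs.

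The consequence is modest. The other listed features and the graphs still allow some judgement of strength, the protocol claims only preliminary evidence, and no test or threshold depends on the overlap wording.

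**What to change.** In the Data analysis part of section 6, redefine overlap by individual ratings, for each child and for both A1-B and B-A2. Either of two measures would do:

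- the proportion of day pairs in which the B rating is not better than the rating in the adjacent phase (1 − NAP). With complete data each contrast has 14 × 35 = 490 pairs. NAP counts a tied pair as one half, so the handling of ties should be stated; or
- the proportion of one phase's ratings that fall within the range of the adjacent phase.

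Report the chosen proportion descriptively beside each graph. The defect does not call for a test or an interval.

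The cost is one reworded definition and a few lines of calculation on ratings already being collected, with no added burden on families. The drawback is that some contrasts may look less favourable than their means suggest.
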